8.5. Subject Withdrawal Criteria

An early termination occurs when a subject who provides written informed consent ceases participation in the study, regardless of circumstances, before the completion of the study. Subjects may be voluntarily discontinued from study medication or withdrawn from the study at any time for any reason. In addition, the Principal Investigator or Medical Monitor may discontinue the study drug administration or terminate a subject's study participation due to any of the following reasons:

- AE (e.g., not compatible with study continuation)
- Non-compliance with study drug
- Lack of efficacy (e.g., IOP exceeds 34 mmHg in either eye after randomization)
- Progressive disease

- Protocol deviation (e.g., not fulfilling eligibility criteria)
- Pregnancy
- Voluntary withdrawal by subject at any time for any reason
- Lost to follow-up (e.g., no contact is possible)
- Death
- Other

If the study drug administration is discontinued prior to Visit 5, they should be encouraged to still participate in follow-up study visits until Visit 5 on an observational basis.

[figure not shown]
If the study drug administration is discontinued prior to Visit 5, then to the extent possible, all procedures for Early Termination will be performed on the day of early drug discontinuation as per [Table 3](#) (for adult subjects) or [Table 4](#) (for pediatric subjects). Subjects who are discontinued from the study early will not be replaced.

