## 6.2. Handling of Missing Data

### 6.2.1. Efficacy Measures

For subjects with the use of any non-study IOP-lowering therapy to lower IOP, unless otherwise specified, the IOP data collected after the non-study IOP-lowering therapy will be censored (treated as missing) in efficacy analyses in both double-masked and open-label periods.

For efficacy measures during double-masked period,

- For each IOP endpoint, no imputation is needed for the analysis on observed cases using the mixed-effects model for repeated measures (MMRM). Sensitivity analysis will be performed using a Pattern-Mixture Model (PMM) approach.
- In the PMM approach, Multiple Imputation (MI) with mixed missing data mechanisms will be used to investigate the appropriateness of the missing at random (MAR) assumption for missing values resulting from censoring due to the use of IOP-lowering rescue therapy, or resulting from study discontinuation due to lack of efficacy or AE.

For efficacy measures during open-label treatment period, no inferential analysis will be performed. Summary statistics will be provided for IOP and mean diurnal IOP for each scheduled visit, using observed data.

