**Table 8: Overview of Primary and Sensitivity Analysis Methods**

| Primary or Sensitivity Analysis | Statistical Method        | Analysis Population | Handling of Missing Data |
|---------------------------------|---------------------------|---------------------|--------------------------|
| Primary Analysis                | MMRM                      | FAS                 | Observed cases           |
| Sensitivity Analyses            | MMRM                      | PPS                 | Observed cases           |
|                                 | PMM with delta-adjustment | FAS                 | MI                       |

Abbreviations: FAS = full analysis set; MI = multiple imputation; MMRM = mixed-effects model for repeated measures; PMM = pattern-mixture model; PPS = per protocol set.

To assess the sensitivity to departure from MAR assumption, a PMM with delta-adjustment will be applied, as follows:

- a. Use Markov chain Monte Carlo (MCMC) to create monotone missingness first. Then obtain standard multiple imputations under MAR assumptions for missing IOP values using monotone regression. The missing data are filled in and 50 complete datasets are created. The seed that will be used in the SAS program is 13546.
- b. For each IOP value that had been missing because of (1) censoring after having received IOP-lowering rescue therapy; or because of (2) early study discontinuation due to lack of efficacy or AE, regardless of treatment arm, adjust these values by adding delta to the imputed values, where delta = 1.0 mmHg. The seed that will be used in the SAS program is 13546.
- c. Each of the 50 complete datasets will then be analyzed separately using the same MMRM as used for the primary analysis.
- d. The estimates obtained from the MMRM analysis of each complete dataset are combined for inference purposes.
- e. Repeat step b, c, d, with delta = 2.0, 3.0, 4.0, and 5.0 mmHg. The larger the value of delta that is required to reverse the conclusion of the primary analysis, the more robust the conclusion is considered to be.

The main part of the SAS code for the specified MMRM analysis and PMM are provided in [Appendix A](#) and [Appendix B](#), respectively.

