For the primary endpoint, in addition to the two types of sensitivity analyses described above, if the overall rate of study drug discontinuation due to lack of efficacy or AE is greater than 10% and the difference between the rate in the DE-117 and Timolol arms is greater than 5 percentage points, a trimmed mean analysis ([Permutt et al., 2017](#)) will be conducted as a sensitivity analysis.

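### Withdrawal for progressive disease is left out of the reasons that earn a delta in the pattern-mixture analysis and that count toward the trimmed-mean trigger

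*SAP*

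**What the plan says.** Protocol 8.5 lists the reasons for which study drug or study participation may be stopped. Lack of efficacy is one item, with an IOP threshold as its example. "Progressive disease" is another item, with no definition. AE is a third.

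Three places in the SAP use a shorter list:

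- **SAP 6.2.1** names two groups in which the pattern-mixture model (PMM) examines MAR. The first is "missing values resulting from censoring due to the use of IOP-lowering rescue therapy". The second is worded "or resulting from study discontinuation due to lack of efficacy or AE".
- **SAP 8.1.1.2, step b**, adds delta to two groups of missing values: those missing because of "censoring after having received IOP-lowering rescue therapy", and those missing because of "early study discontinuation due to lack of efficacy or AE, regardless of treatment arm". The instruction is to "adjust these values by adding delta to the imputed values, where delta = 1.0 mmHg", and step e says "Repeat step b, c, d, with delta = 2.0, 3.0, 4.0, and 5.0 mmHg".
- **The trimmed-mean paragraph at the end of SAP 8.1.1.2** adds that analysis "if the overall rate of study drug discontinuation due to lack of efficacy or AE is greater than 10" percent and the two arms differ by more than 5 percentage points. It has no rescue component.

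SAP 7.1 tabulates discontinuation by primary reason. SAP 10.3 removes LOCF because the PMM is judged sufficient to test the robustness of the MMRM.

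**The concern.** Step b is meant to penalise missing values that may reflect treatment failure. Withdrawal for progression is plausibly of that kind in a glaucoma trial, but the stated rule does not reach it unless the subject also has rescue-censored values or is recorded under AE or lack of efficacy. Two similar subjects could then be treated differently because the investigator chose one of two neighbouring reasons.

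With LOCF gone, the PMM is the only unconditional check on the MAR assumption, and the trimmed-mean analysis is the conditional one. Both rely on the same short list. If withdrawals for progression were more frequent on DE-117, the PMM would be slightly too favourable to non-inferiority, and the trimmed-mean analysis might not be run when it was needed.

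**Working it through.** The documents give no figure to reproduce on this point: no rate of withdrawal for progressive disease is stated. The check is to trace the rule and then size the gap under assumed counts.

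**Who is affected**

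| Subject with progressive disease as primary reason | PMM | Trimmed-mean trigger |
|---|---|---|
| Stops drug, stays to Visit 5, no rescue | Values observed | Not counted |
| Stops drug, stays, receives rescue | Later values censored and given delta | Not counted |
| Leaves the study, values already censored after rescue | Those values given delta | Not counted |
| Leaves the study, no rescue-censored values | Imputed under MAR, no delta | Not counted |
| Same event recorded as AE or lack of efficacy, leaves the study | Given delta | Counted |

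The gap in the PMM is the fourth row. The gap in the trigger is the first four rows.

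**Size in the PMM**

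Inputs: 200 adults per arm and SD 4.0 mmHg (SAP 3.3); delta 1 to 5 mmHg (SAP 8.1.1.2, steps b and e). Assumed: k more fourth-row subjects on DE-117 than on timolol, all missing at the visit in question.

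Adding delta to k more of 200 subjects moves the DE-117 minus timolol difference by approximately

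shift = delta × k / 200.

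| k | delta = 1 | delta = 5 |
|---|---|---|
| 1 | 1 × 1/200 = 0.005 mmHg | 5 × 1/200 = 0.025 mmHg |
| 2 | 1 × 2/200 = 0.01 mmHg | 5 × 2/200 = 0.05 mmHg |
| 4 | 1 × 4/200 = 0.02 mmHg | 5 × 4/200 = 0.10 mmHg |

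For scale, the unadjusted standard error of the difference at one timepoint is 4.0 × √(2/200) = 0.40 mmHg. With k = 0 the shift is zero. With k negative (an excess on timolol) it has the opposite sign.

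**Effect on the trigger**

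On 400 adults, a rate above 10% needs at least 41 discontinuations, and a difference above 5 points needs at least 11 more in one arm than in the other. Both conditions must hold.

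- Lack of efficacy or AE, 25 v 15: 40/400 = 10.0%; 12.5% − 7.5% = 5.0 points. Neither limit is exceeded, so the trigger does not fire.
- Adding progressive disease, 2 v 0, gives 27 v 15: 42/400 = 10.5%; 13.5% − 7.5% = 6.0 points. Both limits are exceeded, so it fires.

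These counts are illustrative and chosen to lie at the threshold.

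**The case against.** The strongest reply is that very few subjects fall in the gap. Delta does not depend on the withdrawal reason once rescue therapy has been given. Subjects who stop drug are encouraged to stay to Visit 5, and those who stay without rescue contribute observed values. Early-termination procedures include IOP, and the SAP Table 4 windows can map that reading to an analysis visit. Protocol 12.1.1 allows a clinically significant worsening of a pre-existing condition to be an AE, so some cases would be recorded there. Advanced glaucoma is excluded, visual fields are scheduled only at screening, and ophthalmoscopy is not scheduled between Baseline and Month 3. The main scheduled sign of failure in that interval is IOP, which is the protocol's own example of lack of efficacy. All of this stands and keeps the point small. It does not close the gap: leaving without rescue is possible, recording the event as an AE is discretionary, and the trigger has no rescue component.

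Several stronger readings are tempting, and the documents do not support them.

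- *Only lack of efficacy or AE leads to delta.* This is true of the trigger, but step b also covers every value censored after rescue.
- *Anyone withdrawn for progression is imputed as a typical subject.* Only the fourth row is imputed without delta, and step a uses MCMC and monotone regression, which draw on the subject's own earlier IOP.
- *The trial's chance of meeting its nine-timepoint rule falls.* That rule decides the primary observed-case MMRM, which imputes nothing and is untouched. The PMM is read as a tipping-point series. Nor can one subject be missing all nine timepoints, because the full analysis set requires a post-baseline IOP.
- *Progressive disease means worsening glaucoma and is a fixed case-report code.* The protocol does not define the term, and the case report form is not in the documents. The reading is reasonable, but it is an inference.

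The SAP refers to Appendix B for the PMM code. The text available for review does not contain it, so a classification there cannot be ruled out.

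**Conclusion.** The gap is real and minor. Protocol 8.5 separates progressive disease from lack of efficacy, the three SAP passages omit it, and no visible text assigns it to either named reason. It affects the PMM sensitivity analysis and the trimmed-mean trigger, not the primary analysis.

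The PMM range of 0.005 to 0.10 mmHg rests on an assumed excess of 1 to 4 unrescued study withdrawals on DE-117. The true number may be zero, balanced or in the other direction, and over 3 months it is probably very low. The trigger matters only if the counts lie close to both limits. The reason to act is that the correction costs almost nothing and removes a dependence on coding choice that could not be settled credibly once treatment is known.

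**What to change.** Before unmasking, replace *lack of efficacy or AE* with *lack of efficacy, progressive disease or AE* in SAP 6.2.1, in step b of SAP 8.1.1.2 and in the trimmed-mean trigger, and make the code in Appendix B agree.

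The cost is two added words in three places, with no new data and no new method. Step b refers to leaving the study and the trigger to stopping study drug; if that difference is not intended, the same revision can settle it.

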### **3.4. Visits and Assessments**

There are 5 scheduled visits for pediatric subjects and 9 scheduled visits for adult subjects. Assessments at each visit and the time/visit window for each post-baseline assessment are specified in the Assessment Schedule for adult ([Table 1](#)) and pediatric subjects ([Table 2](#)), respectively.

If the study drug administration is discontinued prior to Visit 5 (end of the double-masked treatment period), the subject should be encouraged to still participate in follow-up study visits until Visit 5 on an observational basis. For subjects whose study participation is terminated prior to Visit 8 (Month 12), to the extent possible, all assessments scheduled for Visit 8 (Month 12) will be performed at the Exit Visit.

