**Noninferiority criteria for primary endpoint:** With respect to the primary study objective, noninferiority of DE-117 to Timolol is achieved if the upper limit of the two-sided 95% confidence interval for the difference in the mean IOP (DE-117 minus Timolol) is  $\leq 1.5$  mmHg at all nine timepoints and  $\leq 1.0$  mmHg at a majority (five or more) of the nine timepoints.

Superiority of DE-117 to Timolol for the primary efficacy endpoint is achieved if the upper limit of the two-sided 95% confidence interval for the difference in the mean IOP (DE-117 minus Timolol) is  $< 0$  mmHg at all nine timepoints.

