#### 8.1.1.2. Sensitivity Analyses

For the primary endpoint and the key secondary endpoints, sensitivity analyses will be performed to assess the robustness of the results from the primary analysis. The sensitivity analyses consist of two types: (1) assessment based on the PPS and (2) a pattern-mixture model (PMM) approach ([Table 8](#)). Unless otherwise specified, for subjects who receive IOP-lowering rescue therapy, any IOP values collected after the receipt of rescue therapy will be censored (i.e., treated as missing) in the analyses.

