### **10.3. Sensitivity Analysis of the Primary and Secondary Efficacy Endpoints**

Protocol Amendment 1 (Version 1.1) Section 14.5, Handling of Missing Values, specified a sensitivity analysis of the primary efficacy endpoints and the secondary binary IOP endpoints (Month 3) in which missing values would be imputed using the last-observation-carried-forward (LOCF) approach. The LOCF approach is removed from the sensitivity analyses because the PMM generalizes the MMRM to include mixed missing data mechanisms beyond the MAR assumption of the MMRM. Thus, the PMM is sufficient to evaluate the robustness of the results from the MMRM.

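### The pattern-mixture analysis adds the same delta in both arms, so it barely tests non-inferiority unless DE-117 has more of the shifted missing values; add a two-way grid of arm-specific deltas

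*SAP*

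**What the plan says.** For the primary and key secondary endpoints, SAP 8.1.1.2 states: "The sensitivity analyses consist of two types: (1) assessment based on the PPS and (2) a pattern-mixture model (PMM) approach". By Table 8, the per-protocol analysis is again an MMRM on observed cases. The pattern-mixture model is therefore the only analysis departing from missing at random (MAR) that is always run.

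Step b selects imputed values that were missing through censoring after rescue, or through leaving the study for lack of efficacy or an adverse event (below, the eligible values). It then says: "regardless of treatment arm, adjust these values by adding delta to the imputed values, where delta = 1.0 mmHg". Step e repeats this at 2.0, 3.0, 4.0 and 5.0 mmHg and gives the reading rule: "The larger the value of delta that is required to reverse the conclusion of the primary analysis, the more robust the conclusion is considered". No arm-specific delta, two-way grid or reference-based imputation is described.

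SAP 6.2.1 gives the purpose: multiple imputation "will be used to investigate the appropriateness of the missing at random (MAR) assumption" for these values. SAP 10.3 drops LOCF on the ground that "Thus, the PMM is sufficient to evaluate the robustness of the results from the MMRM". A trimmed-mean analysis is added for the primary endpoint only, if the "overall rate of study drug discontinuation due to lack of efficacy or AE is greater than 10% and the difference" between the arms exceeds 5 percentage points.

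**The concern.** Adding the same amount in both arms largely cancels in the difference. What is left depends on which arm has more eligible values, not only on how badly those subjects did. Equal numbers of missing values do not imply equal departures from MAR: DE-117 subjects who were rescued or left could be worse than imputed by more than their Timolol counterparts. For a non-inferiority claim, that is the departure that matters most.

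With balanced eligible missingness, delta can go to 5 mmHg and the estimate does not move. With more on Timolol, raising delta makes non-inferiority easier to show. Step e would report both outcomes as robust. The trimmed mean does not fill the gap: it cannot run when discontinuation is balanced, and when it does run it is not an arm-specific tipping point.

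**Working it through.** **Inputs from the documents.** 200 per arm, SD 4.0 mmHg, correlation 0.6, true difference 0, margin 1.5 mmHg, two-sided 95% interval (Protocol 14.3.1, SAP 3.3). Success (SAP 8.1.1.1.1) needs an upper limit of at most 1.5 mmHg at all nine time points and of at most 1.0 "mmHg at a majority (five or more) of the nine timepoints".

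**Assumptions.** The documents give no rates of eligible missingness, so these are varied. The model adjusts for baseline IOP. If the correlation of 0.6 also holds with baseline, the adjusted SD is 4.0 × √(1 − 0.36) = 3.2 and the residual correlation is (0.6 − 0.36)/(1 − 0.36) = 0.375. Both SDs are carried through.

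**The plan's own figure.** The plan gives no figure for the pattern-mixture analysis. Its 90% power is not disputed here and serves only to judge which SD is more realistic. The full nine-point rule with no missing data gives 72.3% at SD 4.0 and correlation 0.6, and 94.2% at SD 3.2 and correlation 0.375. SD 3.2 is nearer the plan.

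**Shift.** With eligible shares pD and pT and deltas dD and dT, the difference moves by dD × pD − dT × pT. With a common delta this is delta × (pD − pT). The variance in each arm becomes SD² + p(1 − p)d², and the upper limit is the shift plus 1.96 × SE when the observed difference is 0.

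Worked case, SD 4.0, 10% eligible in each arm:
- No shift: 1.96 × √(32/200) = 0.78.
- Delta 5 in both arms: variance per arm 16 + 0.09 × 25 = 18.25; upper limit 0 + 1.96 × √(36.5/200) = 0.84.
- Delta 5 on DE-117 only: 0.50 + 1.96 × √(34.25/200) = 1.31.

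Upper limits (mmHg) at a single time point:

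| Eligible share, DE-117 / Timolol | SD | (0,0) | (5,5) | (5,0) |
|---|---|---|---|---|
| 10% / 10% | 4.0 | 0.78 | 0.84 | 1.31 |
| 10% / 10% | 3.2 | 0.63 | 0.69 | 1.16 |
| 15% / 10% | 4.0 | 0.78 | 1.10 | 1.57 |
| 10% / 15% | 4.0 | 0.78 | 0.60 | 1.31 |

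In the last row the planned delta of 5 lowers the limit, because the shift is 5 × (0.10 − 0.15) = −0.25 mmHg.

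**Simulation of the full criterion.** 3,000 trials per scenario; eligible values at Week 6 and Month 3, none at Week 1; missingness unrelated to outcome; 50 regression imputations by arm and clock time; Rubin's rules; arm means in place of the MMRM. Under MAR about 68–72% of trials pass at SD 4.0 and 92–94% at SD 3.2. Entries are the share of passing trials reversed; ranges cover fixed and random eligible counts.

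| Eligible share, Week 6 / Month 3 | Delta (DE-117, Timolol) | SD 4.0 | SD 3.2 |
|---|---|---|---|
| Both arms 5% / 10% | (2,2) | 0–3% | 0–2% |
| | (2,0) | 18–20% | 11–12% |
| | (5,5) | 4–9% | 3–6% |
| | (5,3) | 21–23% | 15–17% |
| | (5,0) | 53–55% | 48% |
| Both arms 2% / 5% | (5,5) | 2–5% | 1–3% |
| | (5,0) | 23–24% | 13–14% |
| Both arms 1% / 2% | (5,5) | 1–3% | 1–2% |
| | (5,0) | 8% | 4% |
| DE-117 10% / 15%, Timolol 5% / 10% | (5,5) | 39% | 31–34% |
| DE-117 5% / 10%, Timolol 10% / 15% | (5,5) | 0–1% | 0–1% |
| | (5,0) | 56% | 48–50% |

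A simpler calculation, with eligible missingness building up to 10% per arm at Month 3, gives for delta 5: 5.3% (common) against 60% (DE-117 only) at SD 4.0, and 2.9% against 52% at SD 3.2.

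**First key secondary endpoint** (Month 3 mean diurnal IOP), both arms 5%/10%, delta 5: 0–1% (common) against 20–21% (DE-117 only) at SD 4.0; 0% against 3–5% at SD 3.2.

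**Trimmed-mean trigger.** Drug discontinuation of 10% and 16% gives 13% overall and a 6-point gap, so it runs. At 13% in each arm it does not.

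**The case against.** A common delta is a coherent model. The plan ties the departure from MAR to the reason for missingness, and the same penalty for the same reason in each arm is defensible. Nothing in the documents predicts a larger departure on DE-117. This is why the common-delta analysis should stay. It does not justify reading its tipping point as general robustness.

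The simulation has a true difference of 0 and missingness unrelated to outcome. Every reversal therefore overturns a correct conclusion. This stands: the figures show how strongly each analysis can stress the result, not how often the plan would falsely reassure.

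The (5,0) setting is an extreme corner, and SD 4.0 exaggerates reversals because many trials there pass only narrowly. At SD 3.2 with both arms at 5%/10%, a trial observing exactly no difference has upper limits of 0.63, 0.90 and 1.16 at the three visits under (5,0). Six of nine are then at most 1.0, and it still passes. This also stands, so the SD 3.2 and (5,3) rows deserve the most weight. There the contrast is still 15–17% against 3–6%.

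Eligible values may be few. SAP 3.4 says of anyone stopping drug before Visit 5 that "the subject should be encouraged to still participate in follow-up study visits until Visit 5 on an observational basis", and unrescued IOP then stays in the analysis. SAP 7.1 also tabulates discontinuation by reason and arm, which gives a rough view of the imbalance but not of rescue-censored values by visit.

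The superiority tests and the endpoint in eyes with baseline mean diurnal IOP below 25 mmHg were not simulated. The Week 1 endpoint has no eligible values under the pattern assumed. The evidence is therefore strongest for the primary endpoint.

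**Conclusion.** The concern holds. As written, the pattern-mixture analysis is close to flat when eligible missingness is balanced, and it moves toward non-inferiority when Timolol has more. In those cases surviving delta 5 says little about a departure that is larger on DE-117. When DE-117 has more eligible values, the planned analysis works as a stress test.

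The mechanism follows directly from step b. The sizes rest on assumed missing rates, on imputation by arm (the Appendix B code is not in the public text) and on arm means standing in for the MMRM. The issue shrinks to little at 1–2% eligible. It concerns the strength of the robustness statement, not the primary decision. It is an improvement to consider, held with medium confidence.

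**What to change.** Keep the common-delta analysis, which is the diagonal of a two-way grid. Beside it, specify deltas of 0 to 5 mmHg separately in each arm, including DE-117 above 0 with Timolol at 0, for the primary and key secondary endpoints to which SAP 8.1.1.2 already applies the model. If output must be limited, do the primary endpoint first.

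Report where each endpoint's own non-inferiority or superiority criterion fails; for the primary endpoint that is the full two-part rule. Add the number of eligible missing values by arm and visit. Reword step e so that robustness is read from the grid, and qualify the claim of sufficiency in SAP 10.3. Fix all of this before unmasking so that the deltas are not chosen after the fact.

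The cost is a second loop over the same 50 imputed datasets (6 × 6 = 36 cells instead of 5), a grid table per endpoint, a table of counts and edits to steps b and e and to SAP 10.3. No new data are needed. The drawbacks are extra programming and output, with more tables where both non-inferiority and superiority are tested, and a robustness result that may look less favourable.
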